#### **13.3 Potential Patient Benefits**

The potential benefits of this applicator and treatment are:

Decreased likelihood of tumor recurrence

Reduction in the amount of radiation delivered to normal breast and organ tissue

Elimination of delays in systemic/local therapy

Reduction of treatment time

#### 13.4 Informed Consent

Informed consent must be obtained prior to commencing any research procedures. This will typically be at the second visit. The PI shall seek such consent only under such circumstances that provide the prospective patient opportunity to consider whether or not to participate and that minimizes the possibility of coercion or undue influence. The information given to the patient, or the representative, shall be in a language understandable to the subject or representative. The informed consent document may not include any exculpatory language through which the subject or representative is made to waive any of the subject's legal rights or releases, or appears to release the investigator, the sponsor or the institution from liability for negligence.

##### **Non-English Speaking Patients**

Where informed consent is documented in accordance with §46.117(b)(1), the written consent document should embody, in language understandable to the subject, all the elements necessary for legally effective informed consent. Subjects who do not speak English should be presented with a consent document written in a language understandable to them.

1. An IRB approved short form written document shall be presented in a language understandable to the subject.
2. The IRB approved English informed consent document may serve as a summary.
3. An interpreter fluent in English and the patient's language shall present the English IRB consent form offered, read it and orally present it to the patient.
4. Through the interpreter, the investigator will explain participation is voluntary and all aspects of the study, the purpose of the study, treatment plan, procedures, risks, benefits, alternatives, and the right to refuse and withdraw at any time without penalty in lay language.
5. Through the interpreter the investigator will answer any questions the patient may have.
6. The investigator shall give the subject adequate opportunity to take the IRB approved English informed consent document home for review by family and/or friends who are fluent in English and the language understandable by the patient.
7. If the patient decides to participate in the study, he/she will be asked to sign the short form document.
8. The IRB approved informed consent document will be signed by the person obtaining consent as authorized under the protocol.
9. The written short form document and the English informed consent document will be signed by the witness.

10. When the person obtaining consent is assisted by a translator, the translator may serve as a witness.
11. A copy of the signed IRB approved short form document and the English informed consent document will be given to the subject and this will be documented in the patient's medical record.
12. Through the interpreter, the investigator shall inform all patients they have the right to refuse study participation and withdraw their participation at any time without penalty and will be treated without prejudice

### **13.5 Institutional Review Boards**

This protocol and an informed consent form will be approved initially and reviewed at least annually by an institutional review board (IRB) constituted according to regulatory and institutional requirements. The IRB granting the initial approval shall be responsible for continuing review and approval of this study including the informed consent form. A copy of the IRB's dated approval will be retained in the study files.

### **13.6 Economic/Financial Considerations**

The treatment modalities of this protocol (brachytherapy) are standard of care and so will be paid per usual, by insurance or government agencies (charity care, Medicare, Medicaid). Patients will be responsible for their insurance required co-pays and deductibles.

## **14. DATA HANDLING AND RECORD KEEPING**

### **14.1 Source Documents**

Adequate original records will be maintained for the study, including (but not limited to) patient medical and surgical records, data collection forms, exam printouts, signed informed consent forms, device use records, and adverse event reports. All original source documentation will remain at the investigational site.

All investigational sites **MUST PROVIDE ACTUAL COPIES OF:**

The pathology report used to establish the diagnosis of breast cancer **AND** the radiation treatment summary report from the site.

NOTE: The patient's name and any other individually identifiable information will be removed and replaced with the patient's study identification number.

### **14.2 Case Report Form Completion**

Case Report Forms (CRFs) can be found in the appendix of this study for each patient enrolled in the study. CRFs may be found in Appendix 8. The appropriate CRF will be completed in a legible manner in ink after each study examination. (NOTE: Any corrections will be made by drawing a single line through the incorrect entry, entering the correct information, initialing and dating the change.)

All clinical data generated in the study will be submitted to Rutgers Cancer Institute of New Jersey for quality assurance review, data entry and statistical analysis. All forms will be reviewed for completeness and evident recording errors. Questions or queries will be resolved

by contact with the clinical sites.

### **14.3 Reports**

The investigator will submit progress reports at least once yearly and at the completion of the study to the IRB. The investigator will also submit any additional reports as requested by the IRB as a condition of study approval (e.g., safety reports, etc.).

Throughout the accrual and active treatment periods of the trial, progress reports will be prepared and presented to the Data Safety Monitoring Board (DSMB) as necessary but minimally at 6-month intervals. These reports will include an assessment of toxicities, second primary cancers and on-therapy deaths. For serious and/or unanticipated adverse events, the decision to continue the registry study will be evaluated by the DSMB as appropriate (refer to Appendix 4 for adverse event reporting criteria). After accrual is closed, adverse events and other information will be presented to the DSMB together with interim analysis results. Interim analysis will be performed annually once half of the patients have been enrolled.

### **14.4 Records Retention**

The investigator will maintain accurate, complete and current study records during the clinical study.

## **15. STATISTICAL CONSIDERATIONS**

### **15.1 Patient Accrual**

Following IRB approval at all participating accrual sites, an accrual rate of 5-10 patients per month is anticipated.

## 15.2 Primary and Secondary Hypotheses

The primary hypothesis of this study is that the delivery of short-course APBI using a breast brachy-therapy device will result in a serious toxicity rate that is similar to that reported for conventional fractionation schemes for APBI. The secondary endpoints are that local control and cosmesis will be similar to those reported for this patient population using standard of care breast conservation therapy. Specific stopping criteria for toxicity have been defined in Section 15.3.

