## 15.3 Sample Size Justification

The treatment will be considered unsafe if a 2-year serious toxicity rate exceeding 10% cannot be excluded with the 95% interval. Serious toxicity in this study is defined as toxicity greater than grade 2 using CTCAE v4.0 criteria. To be scored as a serious toxicity counting toward the primary endpoint, the toxicity must have a “probable” or “definite” attribution to the study treatment. In a cohort of 200 patients, there should be 11 or fewer serious toxicities to exclude a rate of 10% using the upper limit of the 95% confidence interval.

The primary purpose of this trial is to ensure that the delivery of short-course accelerated partial breast irradiation (APBI) will result in a rate of serious toxicity that is similar to that reported for conventional fractionation schemes. Specifically, the treatment will be considered safe if we are confident that the 2-year serious toxicity rate doesn't exceed 0.10. Assuming that the probability of serious toxicities with the conventional procedure is 0.03, with a sample size of 200 patients, if we observe up to 11 serious toxicities, the upper 95% confidence limit will not exceed 0.10. The relative threshold toxicity rates for different sample sizes has been generated and is available for review from the PI.

A secondary endpoint is local control. We will follow patients until the last enrolled patient has a minimum follow-up of 2 years; thus the expected median follow-up of the study population will be 3-4 years. This will allow for a Kaplan-Meier estimate of local control at 3 years. We expect local control to be greater than 95%.

In addition to toxicity, cosmesis will be followed and evaluated as a secondary endpoint. Cosmesis will be evaluated by determining the number and percent of patients within each response category (Excellent, Good, Fair, Poor) at yearly intervals. Additionally, calculating the distribution of responses after collapsing into Excellent/Good versus Fair/Poor categories will be performed. Associations between dichotomous cosmetic outcomes (Excellent/Good versus Fair/Poor) and treatment related variables will be explored.

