## 15.9 Interim Analysis

See Section 15.3.

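### Sections 15.2 and 15.9 send the reader to 15.3 for toxicity stopping criteria and the interim analysis, but 15.3 prints only the end-of-study rule of 11 in 200

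*Combined protocol and SAP*

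**What the plan says.** All references are to the combined protocol and SAP.

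- **15.2** tells the reader: "Specific stopping criteria for toxicity have been defined in Section 15.3".
- **15.9**, the whole interim analysis section, reads "See Section 15.3".
- **15.3** gives the final criterion: with 200 patients, "if we observe up to 11 serious toxicities, the upper 95% confidence limit will not exceed 0.10". Sections 1.4.1 and 5.1.1 repeat the 11-of-200 rule. To count, a toxicity must be above grade 2 with probable or definite attribution. Section 15.3 then adds: "The relative threshold toxicity rates for different sample sizes has been generated and is available for review from the PI".
- **14.3** requires DSMB progress reports, including toxicities, at least every 6 months during accrual and treatment. For serious or unanticipated events, "the decision to continue the registry study will be evaluated by the DSMB as appropriate". It also says: "Interim analysis will be performed annually once half of the patients have been enrolled". The only sentence that sends interim results to the DSMB is: "After accrual is closed, adverse events and other information will be presented to the DSMB together with interim analysis results".
- **Appendix 4** requires serious adverse events to reach the coordinating centre within 5 days of their becoming known.

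**The concern.** Safety is the primary endpoint of this single-arm study. An IRB, a site or a DSMB member who reads 15.2 will believe that a stopping rule for toxicity exists and can be looked up. Following the reference leads to a rule that applies once, at the end, to 200 patients. It has no look time, interim count or consequence. Section 15.9 sends the reader to the same place and does not cite 14.3, where the look schedule actually stands.

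Two things are at stake. First, the protocol asserts a safeguard that nobody can check or apply from its text. Second, no printed rule pauses accrual once the final criterion is out of reach, so women could still be enrolled after the treatment can no longer be called safe under the plan's own definition.

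**Working it through.** **1. The printed rule reproduces.** Inputs from 15.3: n = 200, limit 10%, 95% interval. The exact two-sided upper limit for x patients is the 0.975 quantile of Beta(x+1, n−x).

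| Count | Exact | Wilson | Agresti-Coull |
|---|---|---|---|
| 11/200 | 9.63% | 9.58% | 9.68% |
| 12/200 | 10.25% | 10.19% | 10.29% |

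All three methods pass 11 and fail 12. At the assumed 3% rate, P(X ≥ 12 of 200) = 0.018. At a true rate of 10%, P(X ≤ 11) = 0.017. The rule is sound, but it is a final rule.

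**2. Interim looks fall during accrual.** Section 15.1 says "an accrual rate of 5-10 patients per month is anticipated", and 3.2 allows three years for accrual (200/36 = 5.56 per month). Annual looks start at 100 enrolled.

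| Accrual per month | First look | Next look | Accrual ends |
|---|---|---|---|
| 5 | 100/5 = month 20 | month 32 | 200/5 = month 40 |
| 5.56 | month 18 | month 30 | month 36 |
| 10 | 100/10 = month 10 | none before closure | 200/10 = month 20 |

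Results therefore exist before accrual closes, while the routing sentence in 14.3 covers only the period after closure.

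**3. The final rule does not fix an interim trigger.** At n = 100, three readings are possible:

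- Re-apply the final rule: the largest passing count is 4 by exact (9.93%) or Wilson (9.84%), and 3 by Agresti-Coull (4/100 gives 10.16%).
- Stop when the exact lower limit exceeds 10%: this needs 17 patients.
- Stop when 11 of 200 can no longer be met: this needs 12 patients.

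Purely as illustration, the first reading used as a stopping boundary would be crossed at a true 3% rate with probability P(X ≥ 5 of 100) = 0.18 or P(X ≥ 4 of 100) = 0.35.

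**4. The 12th patient is a safe trigger on a fixed denominator.** The count of affected patients cannot fall, and imputation can only add to it. With 200 in the denominator, 12 or more gives an exact upper limit of at least 10.25%, so no trial paused there could still pass.

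This fails if the trigger follows a shrinking denominator. The exact rule passes 11 at 193-200 evaluable but only 10 at 180-192. At 190, 11 patients give 10.12%, a fail. But 15.8 imputes missing data. If the 10 missing patients are imputed without an event, the result is 11/200 = 9.63%, a pass. With random imputation at the observed rate, that happens with probability (1 − 11/190)^10 = 0.55.

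**5. Benefit.** The documents give no onset distribution, so this is a range under assumptions. The simulation used 20,000 trials per scenario, 200 patients enrolled evenly and all evaluable, a count every 6 months, visits at 1.25, 12 and 24 months, and a pause at the 12th patient. The table shows the mean number of women not enrolled at true rates of 10/15/20%.

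| Onset and detection | 5 per month | 5.56 per month | 10 per month |
|---|---|---|---|
| Uniform over 24 months, visits only | 5/22/39 | 2/12/27 | 0/0.1/1 |
| Half within 2 months, visits only | 17/46/68 | 11/39/61 | 2/10/19 |
| Uniform, known at onset | 17/46/66 | 11/38/58 | 1/6/15 |

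The third row matters because 7.6 also says adverse events are monitored continuously. At the assumed 3% rate, 0.3% of trials or fewer were paused during accrual.

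**The case against.** **Monitoring already exists.** This stands in part. Section 14.3 gives 6-monthly toxicity reports and DSMB review of continuation. Appendix 4 adds prompt SAE reporting, and its examples overlap with toxicity above grade 2. A reader might infer from the missing boundary that toxicity goes unwatched during accrual; the documents do not support that. What they lack is a number and a consequence.

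**The PI holds the thresholds.** A reader might infer that these do not exist, or that they would wrongly stop 18% or 35% of acceptable trials. Neither follows. Section 15.3 does not say whether they are interim boundaries or passing counts for other final sample sizes, so those percentages only show how much the reading matters.

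**A pause rule is a preference and adds no new criterion.** It is true that a DSMB could work out the 12th-patient point itself. But the plan does not ask for a patient-level count of qualifying toxicities, and the change is small. It is also true that this is no early-warning rule: 8 of 30 patients (27%, exact lower limit 12.3%) would not trigger it. The benefit also depends on onset timing that the documents do not give.

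**A pause could cost power.** This is correct for a trigger that follows the evaluable number, because of the imputation sentence in 15.8. A blanket claim that no power is lost would be wrong. The guarantee holds only with the denominator fixed at 200.

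**Conclusion.** The concern holds as an unresolved cross-reference with a safety consequence. Sections 15.2 and 15.9 promise stopping criteria and an interim analysis in 15.3, and neither is printed there. The 11-of-200 figure itself is correct, and oversight during accrual exists but is discretionary.

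In the visits-only scenarios, a pause at the 12th qualifying patient spares about 0 to 68 enrolments across 5-10 patients per month and true rates of 10-20%. It spares almost none at 10 per month with uniform onset. These sizes rest on assumed onset patterns. The textual defect and the need to correct it do not depend on the simulation. The change should be made.

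**What to change.** **(a) Make the text consistent.** Either reword 15.2 so that it does not claim criteria that are not printed, or print the PI-held thresholds in 15.3 with their purpose, interval method, denominator and resulting action. Have 15.9 cite 14.3. State in 14.3 that interim results obtained during accrual also go to the DSMB.

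**(b) Add a curtailment rule to 14.3 and 15.9.** Each 6-monthly DSMB report tabulates the number of patients, not events, with a qualifying toxicity: above grade 2, probable or definite attribution, within 2 years of device removal (the time origin in 15.6). Accrual is suspended pending a DSMB decision when the final rule can no longer be met. With the printed denominator of 200, that is the 12th such patient. State that this is curtailment of the final rule and not an early-toxicity boundary.

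A lower trigger (by the exact interval, the 11th patient at 180-192 evaluable) should be used only if the sponsor first states that the final denominator excludes patients taken off study (1.5.2.13, 15.8) or lost to follow-up, and reconciles this with imputation in 15.8.

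**Cost.** Wording in 14.3, 15.2 and 15.9 (and 15.3 if the thresholds are printed), and one extra count per report. The downside is a possible accrual pause. If the DSMB then closes the trial, there are fewer data on 3-year local control and cosmesis, and the minimum of 50 multicatheter cases in 15.4 may not be reached.

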## 15.3 Sample Size Justification

The treatment will be considered unsafe if a 2-year serious toxicity rate exceeding 10% cannot be excluded with the 95% interval. Serious toxicity in this study is defined as toxicity greater than grade 2 using CTCAE v4.0 criteria. To be scored as a serious toxicity counting toward the primary endpoint, the toxicity must have a “probable” or “definite” attribution to the study treatment. In a cohort of 200 patients, there should be 11 or fewer serious toxicities to exclude a rate of 10% using the upper limit of the 95% confidence interval.

The primary purpose of this trial is to ensure that the delivery of short-course accelerated partial breast irradiation (APBI) will result in a rate of serious toxicity that is similar to that reported for conventional fractionation schemes. Specifically, the treatment will be considered safe if we are confident that the 2-year serious toxicity rate doesn't exceed 0.10. Assuming that the probability of serious toxicities with the conventional procedure is 0.03, with a sample size of 200 patients, if we observe up to 11 serious toxicities, the upper 95% confidence limit will not exceed 0.10. The relative threshold toxicity rates for different sample sizes has been generated and is available for review from the PI.

A secondary endpoint is local control. We will follow patients until the last enrolled patient has a minimum follow-up of 2 years; thus the expected median follow-up of the study population will be 3-4 years. This will allow for a Kaplan-Meier estimate of local control at 3 years. We expect local control to be greater than 95%.

In addition to toxicity, cosmesis will be followed and evaluated as a secondary endpoint. Cosmesis will be evaluated by determining the number and percent of patients within each response category (Excellent, Good, Fair, Poor) at yearly intervals. Additionally, calculating the distribution of responses after collapsing into Excellent/Good versus Fair/Poor categories will be performed. Associations between dichotomous cosmetic outcomes (Excellent/Good versus Fair/Poor) and treatment related variables will be explored.

## 15.4 Methods for Randomization and Stratification

This study is a non-randomized, single arm study of female patients with early stage, node-negative DCIS or invasive carcinoma receiving APBI following lumpectomy. Thus, there is no randomization or stratification. As a requirement of our study sponsors, a minimum of 50 multicatheter implant cases will be enrolled.

## 15.5 Outcome Measures

The primary endpoint will be measured by the data collected for toxicity and cosmesis as dichotomous variables. Time to local failure will be recorded for secondary endpoint analysis.

## 15.6 Statistical Analysis

All time intervals will be calculated from the date of device removal. Fisher's exact test will be performed to correlate clinical-pathological covariates with toxicity and with cosmesis. The association of variables with LR failure times will be investigated by fitting a parametric model and examining the significance of the parameter estimates. Nonparametric estimates of the survival or recurrence-free distributions or recurrence (failure) distribution will be obtained by life table methods. Tests will be declared statistically significant if the calculated  $P$ -value was  $\leq 0.05$ . All tests appear as 2-sided  $P$ -values.

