## **11. BREAST TOXICITIES**

The primary endpoint of the study is serious toxicity rates. This will be assessed by physical examination at each follow-up visit. To be scored as a serious toxicity counting toward the primary endpoint, the toxicity must have a "probable" or "definite" attribution to the study treatment. Possible reportable toxicities to monitor include (but are not limited to) the following:

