##### **13.1.2 Applicator Implantation**

Complications arising from implantation of the applicator include, but are not limited to: infection, bleeding, loss or impairment of nerve function, swelling (edema), hematoma, fluid accumulation, applicator migration, and histotoxic reactions. Device malfunction may occur after placement requiring the placement of a second replacement device or alternative treatment.

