## 15.8 Compliance and Missing Data

Compliance will be defined as patients who complete the course of radiotherapy in a time frame as described above. If a patient is unable to do so, they will be removed from the study. Data will be accumulated on a daily basis during treatment for each patient, and then in follow-up visits. If by chance there is missing data, it will be imputed based on the population as a whole.

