**APPENDIX 1 – STUDY SCHEMA & EXAM SCHEDULE**  
**STUDY SCHEMA**

**EXAM SCHEDULE**

	Pre-RT Treatment	RT Treatment	Post-RT Treatment	
			2-8 Weeks	Year 1 & 2
Demographics	X			
Physical Exam, including Breast Exam	X		X	X
Pregnancy test 	X			
Applicator Placement	X			
Treatment Planning		X		
Brachytherapy Treatment		X		
Device Removal		X		
Disease Status Evaluation			X	X
BCTOS	X			X 
Harvard Cosmesis	X			X
Digital Photography	X 			X 
Toxicity Evaluations			X	X
Mammogram/MRI 	X 			X 

 MRI optional

 The pre-brachytherapy mammogram should be performed within 6 months of definitive surgery.

[figure not shown]
 Optional; at pre-treatment and 2-year follow up

 Mammography should be performed according to institutional standards of practice and generally performed as a baseline 6-12 months after brachytherapy and repeated annually.

 2-Year Visit

 Women of child-bearing potential only

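### Toxicity that begins between applicator placement and removal has no scheduled graded evaluation and an undefined place in the 2-year primary rate, and no CTCAE-graded baseline is taken

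*Combined protocol and SAP*

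**What the plan says.** Section 15.3 gives the decision rule: "The treatment will be considered unsafe if a 2-year serious toxicity rate exceeding 10% cannot be excluded with the 95% interval". Serious means above CTCAE v4.0 grade 2, and only events with probable or definite attribution count (Sections 11 and 15.3). The rule is then put as a count: "In a cohort of 200 patients, there should be 11 or fewer serious toxicities to exclude a rate of 10" percent.

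On measurement, Section 11 says of this endpoint: "This will be assessed by physical examination at each follow-up visit". Section 7.6 places the first visit 2-8 weeks after treatment, with at least annual visits in years 1 and 2. In Appendix 1 the row "Toxicity Evaluations" is marked in those columns only; the Pre-RT and RT Treatment cells are empty. The complication checklist is on CRF #3, the post-RT form. CRF #1 and CRF #2 do not carry it.

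On timing, Section 15.6 says: "All time intervals will be calculated from the date of device removal". Section 15.8 adds: "Data will be accumulated on a daily basis during treatment for each patient, and then in follow-up visits". It does not say which data these are.

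**The concern.** Placement, the wait before the first fraction and the fractions themselves all come before the stated time origin, and well before the first scheduled toxicity grading. The protocol names risks in that period. Section 13.1.2 begins: "Complications arising from implantation of the applicator include, but are not limited to: infection, bleeding, loss or impairment of nerve function", and goes on to hematoma and fluid accumulation. Appendix 4 gives pneumothorax and wound dehiscence as examples of serious events. An acute event of this kind could have resolved before an examination at 2-8 weeks.

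The baseline problem runs the other way. Seroma, pain and induration can follow the lumpectomy itself. Without a grade taken before radiation, the later judgement that a finding is probably or definitely due to study treatment has no like-for-like comparison.

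Both problems act on a count whose pass limit is 11, so the rules for what enters that count should be explicit.

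**Working it through.** **Coverage, period by period**

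| Period | Scheduled graded toxicity evaluation | What else is recorded |
|---|---|---|
| Before placement | None | Breast examination, Harvard score, BCTOS (Appendix 1, Pre-RT column) |
| Placement to first fraction, 1-5 days (7.4) | None | Planning CT with trapped air and fluid contoured (9.1, 9.2); air/seroma volume (CRF #2) |
| Three fractions, 2-3 days (7.4) | None | Applicator imaging before each fraction (9.6); daily data of unstated content (15.8) |
| Removal to first visit, 2-8 weeks (7.6) | None until the visit | Continuous monitoring (7.6) |
| 2-8 weeks, years 1 and 2 | Yes | CRF #3, #4 and #5 |

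The placement-to-removal window is about 1 + 2 = 3 to 5 + 3 = 8 days, if removal follows the last fraction directly. CRF #4, with onset date, grade and relationship, could be completed in any period, but no scheduled evaluation prompts it before the first visit.

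**Whether serious adverse event reports fill the gap**

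Appendix 4 uses seriousness criteria; the endpoint uses CTCAE grade. They diverge in both directions.
- Appendix 4 classes infection treated only with antibiotics as not serious. CRF #5 grades breast infection needing intravenous treatment as grade 3. Such an event counts for the endpoint but need not be reported as serious unless it meets another criterion, such as hospitalization.
- Appendix 4 gives symptomatic seroma as serious. CRF #5 grades symptomatic seroma managed by simple aspiration as grade 2, which does not count.

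**The plan's threshold**

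Inputs: n = 200, limit 10%, 95% confidence (15.3). The two-sided exact (Clopper-Pearson) upper limit for x events is the 0.975 quantile of Beta(x + 1, n − x).
- x = 11: Beta(12, 189) gives 0.0963, below 0.10.
- x = 12: Beta(13, 188) gives 0.1025, above 0.10.

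The stated limit of 11 is reproduced. Two-sided Wilson (0.0958 and 0.1019) and Agresti-Coull (0.0968 and 0.1029) limits also give 11. A one-sided exact limit would allow 12 (0.0954), so 11 matches the two-sided reading. With X binomial(200, p), P(X ≤ 11) is 0.982 at p = 0.03, the plan's assumption ("Assuming that the probability of serious toxicities with the conventional procedure is 0.03"), and 0.017 at p = 0.10.

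**What misclassified events would do**

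The documents do not give the share of serious toxicity arising before removal, so the inputs here are assumed.

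Events missed: true rate 10%, share m uncounted, counted rate 0.10 × (1 − m).

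| m | Counted rate | P(11 or fewer) |
|---|---|---|
| 0 | 10% | 0.017 |
| 10% | 9% | 0.047 |
| 20% | 8% | 0.117 |
| 30% | 7% | 0.251 |

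Events added: 3% from toxicity after removal, plus a further 1, 2 or 3 percentage points. The addition could be genuine pre-removal events or surgical findings wrongly attributed to radiation; the arithmetic is the same.

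| Added | Counted rate | P(11 or fewer) |
|---|---|---|
| 0 | 3% | 0.982 |
| 1 | 4% | 0.893 |
| 2 | 5% | 0.700 |
| 3 | 6% | 0.458 |

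**The case against.** A reader might infer that early toxicity is excluded from the endpoint. The documents do not say so. Section 15.5 makes toxicity a dichotomous variable and names only local failure as a time to be recorded, so the sentence in 15.6 fixes a clock without expressly shutting out earlier events. Several routes could capture them. Section 7.6 promises continuous monitoring and, although it sits under post-removal follow-up, it mentions deaths on therapy. Appendix 4 asks for all serious adverse events during the study, and Section 7.1 puts a patient on study at registration, before protocol treatment. Section 14.3 sends toxicity reports to the monitoring board throughout active treatment. CRF #4 is not restricted to follow-up visits. This stands: the early events are not shown to be lost. It does not supply a scheduled CTCAE grading or say which events count.

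A reader might also infer that there is no baseline at all. That is too strong. A breast examination, Harvard score and BCTOS (which asks about pain, tenderness, texture and scar tissue) are taken before radiation, and CRF #2 records seroma volume. Only the CTCAE grade is missing.

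Third, it is tempting to size the problem from the registry rates in Section 2.3, 9.5% infection and 13% symptomatic seroma. Those are not grade 3 or higher rates and cannot be set beside an 11-event limit. The two short-course series in Section 2.4 reported no grade 3 toxicity.

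Finally, moving the toxicity origin to placement raises a difficulty of its own. Dosimetric suitability is judged after placement, so some patients will have a device but no protocol radiation (6.2.13, 9.2). Any rule must deal with them.

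**Conclusion.** The point holds as a gap in definition and ascertainment. Graded evaluation of the primary endpoint starts 2-8 weeks after treatment. Events beginning between placement and removal have no scheduled grading and no stated status in the 2-year rate, and post-surgical findings have no graded baseline. Serious adverse event reporting does not substitute, because its criteria differ from CTCAE grade above 2.

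It is not a demonstrated bias toward a safe conclusion. Missed early events would lower the rate, while surgical findings charged to radiation would raise it. Neither share is given, so the size and net direction are unknown. The probabilities above rest on assumed shares and a binomial count in 200 patients. They show how sensitive the rule could be and do not predict what will happen. One event decides the outcome only if the count falls at 11 or 12.

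The change is worth making because it is cheap. The sample size and the limit of 11 are unaffected.

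**What to change.** 1. In Appendix 1, mark toxicity evaluation in the Pre-RT column, as a CTCAE grade at the existing pre-RT examination. Time it before placement, because placement is listed in the same column. Mark it also in the RT Treatment column, at device removal. Put the CRF #3 complication checklist on CRF #1 and CRF #2.
2. In Sections 11 and 15.6, state that in patients who receive at least one protocol fraction, toxicities above grade 2 with probable or definite attribution and onset from applicator placement through 2 years after removal count toward the primary endpoint. State that events in patients who receive a device but no protocol radiation are reported separately. Keep device removal as the origin for local failure.
3. Make clear that the Section 15.8 rule removing patients who do not complete radiotherapy on time does not take them out of this toxicity count.

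The cost is a few sentences, two marks in the schedule and a checklist on two forms. The patient is already examined before radiation and is present at removal, so no visit is added. A few more events may count against the limit of 11. If pre-removal events added 1 percentage point to an underlying 3%, the chance of passing would be 0.893 instead of 0.982. The 3% planning assumption should therefore be stated for the same window.
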